6.5.1. Demographics	10
6.5.2. Baseline Disease Characteristics	10
6.5.3. Historical Illnesses/Pre-existing Conditions.....	10
6.6. Treatment Compliance	10
6.7. Concomitant Therapy.....	10
6.8. Primary and Secondary Biomarker Analyses	10
6.9. Safety Analyses.....	11
6.9.1. Extent of Exposure.....	11
6.9.2. Adverse Events	11
6.9.3. Deaths and Other Serious Adverse Events.....	12
6.9.4. Clinical Laboratory Evaluation.....	12
6.9.5. Vital Signs and Other Physical Findings.....	12
6.9.6. Electrocardiograms	13
6.10. Important Protocol Deviations.....	13
6.11. Interim Analyses	13
6.12. Planned Exploratory Analyses.....	13

[figure not shown]
6.13. Pharmacokinetic/Pharmacodynamic Analyses.....	13
6.14. Clinical Trial Registry Analyses	14
7. References	15

3. Revision History

SAP Version 1 was approved prior to the first visit when a subject receives study drug or any other protocol intervention.

4. Study Objectives

Objectives	Endpoints
Primary	

 Determine PD effect of each dose level of LY3484356 on ER expression, in patients with ER+ early stage breast cancer. 	
 Change in ER expression (as measured by IHC and quantified by H-score) between pre- and on-treatment tumor samples, at each dose level of LY3484356
Secondary	

 Assess PD effect of each dose level of LY3484356 on Tumor cell proliferation. 	
 Change in Ki-67 index (as measured by IHC and expressed by % positive scoring) between pre- and on-treatment tumor samples, at each dose level of LY3484356

 Assess PD effect of each dose level of LY3484356 on PR expression. 	
 Change in PR expression (as measured by IHC and quantified by H score) between pre- and on-treatment tumor samples, at each dose level of LY3484356

 Evaluate safety and tolerability of each dose level of LY3484356. 	
 Incidence of investigator assessed AEs per NCI CTCAE v5.0, at each dose level of LY3484356

 Evaluate PK effect of each dose level of LY3484356. 	
 Plasma concentrations of LY3484356, at each dose level of LY3484356
Exploratory	

Abbreviations: AE = adverse event; CTCAE = Common Terminology Criteria for Adverse Events; ER = estrogen receptor; IHC = immunohistochemistry; NCI = National Cancer Institute; PD = pharmacodynamics; PK = pharmacokinetic; PR = progesterone receptor.

[figure not shown]
5. Study Design

5.1. Summary of Study Design

Study EMBER-2 is a Phase 1, open-label, randomized, pre-operative window study of LY3484356 in post-menopausal women with Stage I to III ER+, HER2- breast cancer who are scheduled for surgery with curative intent. Patients will consent to provide tumor samples obtained at the time of diagnosis and at the time of scheduled surgery or repeat biopsy, for the purpose of biomarker analyses. Patients will then be randomized to one of the dose levels of LY3484356 and receive LY3484356 for 15 days, up to and including the day of scheduled surgery or repeat biopsy (if neoadjuvant therapy is subsequently planned). Tumor samples taken pre- and on-treatment with LY3484356, at the time of diagnosis and scheduled surgery/repeat biopsy, respectively, will then be evaluated for biologic effects, as outlined in the study objectives.

A treatment window of 15 days (-2 to +7 days [ie, a range of 13 to 22 days of LY3484356 treatment]) will be permissible to facilitate flexibility in scheduling of the on-treatment surgery/biopsy. The last dose of LY3484356 will be taken on the morning of surgery/biopsy.

The study schema is illustrated below:

Abbreviations: BC = breast cancer; ER+ = estrogen receptor positive; HER2- = human epidermal growth factor receptor 2 negative.

* Baseline (pre-treatment) tumor tissue collection:

- Adequate archival tissue from diagnostic biopsy is acceptable if collected within 6 weeks prior to consent.
- Fresh biopsy:
 - Required if archival tissue is unavailable/exhausted or was collected >6 weeks prior to consent or while the patient was taking Hormone Replacement Therapy
 - Optional for the purpose of Oncotype DX testing

** Allowable treatment window to facilitate scheduling of on-treatment surgery/biopsy: 15 days (- 2 to + 7 days [ie, a range of 13 to 22 days of LY3484356 treatment will be permissible.])

5.2. Determination of Sample Size

Approximately **30** participants will be assigned equally to the different dose-level cohorts in this study to ensure that conservatively 20 participants, with evaluable biomarker data are ultimately

available for analysis from each cohort. The sponsor may elect to continue accrual until sufficient biomarker data is generated.

The sample size of 20 participants per cohort provides a 90% tolerance probability that the 2-sided 90% confidence interval (CI) for geometric mean of change from baseline in ER expression for each cohort will extend no more than 0.34 from the observed geometric mean in logarithm scale, assuming that the true standard deviation is 0.74 (Kuter et al. 2012) and that the CI is based on the t statistic.

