Abbreviations: AE = adverse event; CTCAE = Common Terminology Criteria for Adverse Events; ER = estrogen receptor; IHC = immunohistochemistry; NCI = National Cancer Institute; PD = pharmacodynamics; PK = pharmacokinetics; PR = progesterone receptor.

Overall Design: Study JZLB is a Phase 1 open-label, randomized pre-operative window study of LY3484356 in post-menopausal women with Stage I to Stage III ER+, HER2- breast cancer who are scheduled for surgery with curative intent. Patients will consent to provide tumor samples obtained at the time of diagnosis and at the time of scheduled surgery or repeat biopsy, for the purpose of biomarker analyses. Patients will then be randomized to either 400 or 800 mg LY3484356 or directly assigned to the 200 mg dose and receive treatment for approximately 15 days, up to and including the day of scheduled surgery or repeat biopsy (if neoadjuvant therapy is subsequently planned). Tumor samples taken pre- and on-treatment with LY3484356, at the time of diagnosis and scheduled surgery/repeat biopsy, respectively, will then be evaluated for biologic effects, as outlined in the study objectives.

Disclosure Statement: This is a biomarker study in patients with early stage ER+ breast cancer with multiple treatment arms of LY3484356.

Number of Participants:

Approximately 90 participants with early stage ER+ breast cancer will be enrolled in this study. Patients will be randomized to either 400 or 800 mg LY3484356 or directly assigned to the 200 mg dose, with approximately 30 patients assigned to each dose level cohort.

Intervention Groups and Duration:

Patients enrolled in this Phase 1 open-label, preoperative study will receive 200 mg, 400 mg or 800 mg of LY3484356 as shown in the table below. Patients will start LY3484356 on Day 1 and continue it daily, up to and including the day of surgery or repeat biopsy on Day 15 (with an allowable window of -2 to +7 days). This pre-surgery/biopsy dose of LY3484356 will be the last dose of LY3484356 treatment on this study.

[figure not shown]
Study Drug	Cohort	Proposed Doses	Dose Schedule, Route of Administration, Duration
LY3484356	A	400 mg	QD, PO, administered for 15 days ^a
LY3484356	B	800 mg	QD, PO, administered for 15 days ^a
LY3484356	C	200 mg	QD, PO, administered for 15 days ^a

Abbreviations: PO = orally; QD = once daily.

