LY3484356 was well tolerated across dose levels in dose escalation, with no dose-limiting toxicities reported during the dose escalation and a maximum tolerated dose was not reached. The most frequently reported treatment-emergent adverse events (TEAEs) at the RP2D (**CCI** n=64) were nausea (**CCI** [REDACTED]), fatigue (**CCI** [REDACTED]), and diarrhea (**CCI** [REDACTED]). Most TEAEs were Grade 1 or 2 in severity. Treatment-related adverse events (TRAEs) at the RP2D were observed in **CCI** [REDACTED] patients, most frequently nausea (**CCI** [REDACTED]), diarrhea (**CCI** [REDACTED]), and fatigue (**CCI** [REDACTED]). Two (**CCI**) patients treated at the RP2D required a dose reduction to

CCI due to a TRAE (CCI). No dose reductions occurred at CCI dose level.

CCI 45 female patients were enrolled in the EMBER-2 trial (J2J-MC-JZLB), and 2 dose levels (CCI) were evaluated in patients with early-stage breast cancer with a treatment period of 15 to 22 days. TEAEs were observed in CCI patients. Most TEAEs were Grade 1 or 2, with the most common TEAEs observed at each dose level CCI

Additional details can be found in the LY3484356 IB.

Window of opportunity trial designs in early stage breast cancer have been utilized to permit the evaluation of in vivo downstream effects of treatment with a specific compound with corresponding samples that otherwise might be difficult to obtain. Ultimately these presurgical studies provide insights into drug-mechanism of action, biologic effects, and dose-PD relationships in order to better inform the development of that drug in the clinic (Arnedos et al. 2019).

Measurement of ER modulation through an immunohistochemistry (IHC) assessment of change in percentage and intensity of ER staining by a H-score is clinically validated (Cohen et al. 2012). Indeed, the degree of target (ER) modulation of fulvestrant was successfully captured utilizing IHC-based assessments of change in both ER and progesterone receptor (PR) expression following treatments ranging from 2 to 6 weeks (Kuter et al. 2012; Robertson et al. 2013; Agarwal et al. 2016).

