4.4. End of Study Definition

The end of the study is defined as the date of the last follow-up visit of the last global participant in the study as shown in the Schedule of Activities (SoA) (Section 1.3). Biomarker data will be evaluated on an interval batched basis. Upon evidence of evaluable primary and secondary endpoint data for 20 patients in each cohort, the study sponsor will have the option to end the trial.

5. Study Population

Prospective approval of protocol deviations to recruitment and enrollment criteria, also known as protocol waivers or exemptions, is not permitted.

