9.2. Sample Size Determination

Approximately 90 participants will be assigned equally to the different dose-level cohorts in this study to ensure that conservatively 20 participants, with evaluable biomarker data are ultimately available for analysis from each cohort. The sponsor may elect to continue accrual until sufficient biomarker data is generated. Participants will be randomized to either 800 mg or 400 mg once daily oral dosing, or directly assigned to the 200 mg dose. See details about randomization in Section 6.3.

CCI
[REDACTED]

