5.3. Method of Assignment to Treatment

Participants will be randomized to one of the dose levels of LY3484356. Randomization will be stratified by tumor histology (infiltrating ductal carcinoma [IDC] versus infiltrating lobular carcinoma [ILC]; as locally determined from the diagnostic tumor biopsy).

6. A Priori Statistical Methods

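### SAP 5.2 gives about 30 as the total to be split equally across dose cohorts, which cannot yield its own target of 20 evaluable per cohort; the protocol has about 30 per cohort and about 90 in total

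*SAP*

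**What the plan says.** SAP section 5.2 opens its sample-size statement with "Approximately 30 participants will be assigned equally to the different dose-level cohorts in this study". The same sentence gives the purpose: at least 20 participants per cohort with evaluable biomarker data, described as a conservative figure. Two further statements follow in that section. One is an open-ended accrual option: "The sponsor may elect to continue accrual until sufficient biomarker data is generated". The other is the precision basis, which begins "The sample size of 20 participants per cohort provides a 90% tolerance probability" and concerns a two-sided 90% t-based interval for the geometric mean change in ER, a half-width of 0.34 on the log scale and an SD of 0.74.

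Protocol section 9.2 uses the same sentence with a different number: "Approximately 90 participants will be assigned equally to the different dose-level cohorts in this study". The synopsis (section 1.1) also gives a total of about 90, "with approximately 30 patients assigned to each dose level cohort". Protocol section 4.4 gives the sponsor an option to end the trial "Upon evidence of evaluable primary and secondary endpoint data for 20 patients in each cohort". Protocol section 2.2 reports that "45 female patients were enrolled in the EMBER-2 trial" at two dose levels.

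**The concern.** As worded, the SAP's 30 is a total to be divided among cohorts, and it is offered as the number that secures 20 evaluable in each. No equal division of 30 over two or more cohorts reaches 20. The statement therefore contradicts itself, and it also disagrees with the protocol.

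Section 5.2 is where a reader of the SAP looks for planned enrolment and for the allowance made for non-evaluable samples. Neither can be recovered from the SAP alone.

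**Working it through.** **Inputs.** From SAP 5.2: stated total 30, target 20 evaluable per cohort, SD 0.74 (log scale), two-sided 90% CI, half-width 0.34, tolerance probability 90%. From protocol 1.1 and 9.2: about 30 per cohort, about 90 in total. Number of cohorts: three in the current protocol. Two is also worked, because the SAP does not mention the 200 mg cohort.

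**1. The plan's own precision figure, at n = 20.**

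Half-width at 90% tolerance = t(0.95, n−1) × SD × √[χ²(0.90, n−1)/(n−1)] / √n. With n = 20 and SD = 0.74 this is 0.342, against the stated 0.34. The probability that the half-width is at most 0.34 is 0.891, against the stated 0.90. The statement reproduces to rounding, so 20 evaluable per cohort is a sound basis.

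**2. The stated total against the target.**

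| | Two cohorts | Three cohorts |
|---|---|---|
| Participants per cohort from 30 | 30/2 = 15 | 30/3 = 10 |
| Minimum total for 20 each, no losses | 2 × 20 = 40 | 3 × 20 = 60 |
| Evaluable fraction needed from 30 | 40/30 = 133% | 60/30 = 200% |
| Total at 30 per cohort | 2 × 30 = 60 | 3 × 30 = 90 |

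Both required fractions exceed 100%, so the target is out of reach whichever cohort count was meant.

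**3. Can 30 be read as per cohort?** Not from the sentence. The protocol uses the same construction with 90, and the synopsis shows that 90 is the total and 30 the number in each cohort. With 30 per cohort the arithmetic works: 20/30 = 67%, which leaves room for up to a third of participants to be non-evaluable. That fraction is implied by the two numbers; neither document states an evaluability rate. Three cohorts of 30 give exactly the protocol's 90.

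**4. Could 30 have been a real design total?** At n = 15 the probability of a half-width of at most 0.34 would be 0.572, and at n = 10 it would be 0.226. The 90%-tolerance half-widths would be 0.413 and 0.548. These figures show only that a total of 30 does not fit the SAP's own precision basis. They are not a forecast for this trial. The 45 participants already enrolled at two dose levels also exceed 30.

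**The case against.** There are four arguments on the other side.

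- **The numeral may be an extraction artefact.** It appears in bold in mid-sentence in the supplied text, which is unusual for a number in running prose, and the text was read from PDF by a program. This stands as a caution: the source PDF should be checked first.
- **The comparison with 90 crosses versions.** The SAP is Version 1, approved on 09-Nov-2020 and before any participant was dosed. The 200 mg cohort and the updated total came with protocol amendment (b). The protocol total in force when the SAP was approved is not in the documents. This explains part of the gap to 90, and also why SAP 5.3 still says "Participants will be randomized to one of the dose levels of LY3484356". It does not explain 30, which fails even for two cohorts.
- **The accrual option cures it.** It limits the consequence, but the sentence presents the stated number itself as what secures 20 per cohort. The option is separate and carries no number.
- **Nothing downstream changes.** Largely true. The figure behind the precision statement is explicit, protocol 4.4 depends on 20 evaluable per cohort, and enrolment has already passed 30. This limits the weight of the point without making the stated sample size correct.

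**Conclusion.** The point holds on the supplied text. SAP 5.2 states a total of 30, against a minimum of 40 for two cohorts or 60 for three with no losses, and against about 90 in the current protocol. The likely cause is that the per-cohort number was written where the total belongs; this is an inference from the match with the protocol's 30 per cohort.

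The conclusion assumes that the numeral was read correctly from the PDF and that there are at least two cohorts. It needs no assumption about the evaluability rate. No loss of precision is claimed. The statement should be corrected because it is the SAP's sample-size statement and is wrong as written, but the practical effect on the trial is small.

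**What to change.** Check the numeral in the source PDF. If it is confirmed, restate SAP 5.2 as approximately 30 participants per cohort, about 90 in total across the three cohorts of the current protocol, to give at least 20 evaluable per cohort. Leave the precision statement unchanged.

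As a separate matter of aligning the SAP with amendment (b), update SAP 5.1 and 5.3 to match protocol 6.3: the 400 mg and 800 mg cohorts are randomised 1:1, and the 200 mg cohort is assigned directly.

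The cost is SAP wording only. Planned enrolment, the analysis and the precision do not change.

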5.3. Method of Assignment to Treatment

Participants will be randomized to one of the dose levels of LY3484356. Randomization will be stratified by tumor histology (infiltrating ductal carcinoma [IDC] versus infiltrating lobular carcinoma [ILC]; as locally determined from the diagnostic tumor biopsy).

6. A Priori Statistical Methods

6.1. General Considerations

Statistical analysis of this study will be the responsibility of Lilly or its designee.

All confidence intervals (CIs) will be given at a 2-sided 95% level, unless otherwise stated.

Log normally distributed variables were log transformed before analysis and summaries reported on the original (anti-log) scale.

Unless otherwise noted, summaries of continuous variables will include a mean, median, standard deviation, minimum, and maximum.

Unless otherwise noted, summaries of categorical variables will include the frequency and percentage (relative to the population being analyzed) of each category.

Additional exploratory analyses of the data will be conducted as deemed appropriate.

6.1.1. Populations

The following analysis populations will be defined for this study:

Intention-to-Treat (ITT) population: will include all enrolled/randomized participants. The ITT analysis will consider allocation of participants to treatment groups as assigned/randomized and not by actual treatment received. This analysis set will be used for all baseline analysis.

Safety population: will include all enrolled/randomized participants who received any quantity of study treatment, regardless of their eligibility for the study. The safety evaluation will be performed based on the first dose of study treatment a participant actually received, regardless of the participant's cohort assignment. The safety analysis set will be used for all dosing/exposure and safety analyses.

Biomarker evaluable (BE) population: will include the subset of participants from the ITT from whom valid baseline and post-treatment result have been obtained. Different biomarker evaluable populations need to be defined for different biomarkers.

6.1.2. Definitions and Conventions

Study treatment refers to LY3484356.

The **date of randomization** is the date the patient was randomly assigned to a study treatment using the IWRS.

The **date of first dose** is the date of the first dose of LY3484356.

The **baseline value of a safety assessment** is the last value observed prior to the first dose of LY3484356.

The **baseline value of an efficacy assessment** is the last value observed prior to the date of enrollment/randomization. If a patient's first assessment occurs after enrollment/randomization but prior to the first dose, this assessment will be used as the baseline.

The **study day of a safety event or assessment** will be calculated as:

- the difference between the date of the event or assessment and the date of first dose plus 1 for all events or assessments occurring on or after the day of first dose. For example, if an event occurs on 08MAR2016 and the date of first dose was 06MAR2016, the study day of the event is 3.
- the difference between the date of the event or assessment and the date of first dose for all events or assessments occurring before the day of first dose. For example, if an event occurs on 05MAR2016 and the date of first dose was 06MAR2016, the study day of the event is -1.

The **study day of an efficacy event or assessment** will be calculated as:

- the difference between the date of the event or assessment and the date of enrollment/randomization plus 1 for all events or assessments occurring on or after the date of randomization.
- the difference between the date of the event or assessment and the date of enrollment/randomization for all events or assessments occurring before the date of randomization.

One **month** is defined as 365/12 days.

Unless otherwise noted, summaries of continuous variables will include a mean, median, standard deviation, minimum, and maximum.

Unless otherwise noted, summaries of categorical variables will include the frequency and percentage (relative to the population being analyzed) of each category.

6.2. Adjustments for Covariates

The stratification factor used in randomization is considered important prognostic factors and are thought to be associated with outcomes. Subgroup analyses based on the stratification factor will be conducted if appropriate.

6.3. Handling of Dropouts or Missing Data

With the exception of dates, missing data will not be imputed.

6.4. Participant Disposition

A detailed description of participant disposition based on all entered participants (participants who have signed the informed consent) will be provided. It will include a summary of the number and percentage of participants entered into the study, rescreened after screen failure, enrolled/randomized in the study, and treated in the study, reasons for discontinuation from study treatment (safety population only), and reasons for discontinuation from study (ITT population only). Reason for discontinuation from both the study treatment and the study will be summarized by pre-determined categories.

6.5. Participant Characteristics

6.5.1. Demographics

Participant demographics will be summarized. Participant demographics will include age, race, ethnicity, height, weight, and body mass index.

6.5.2. Baseline Disease Characteristics

Disease characteristics will be summarized. Disease characteristics will include the following:

- Initial pathological diagnosis
- Disease stage (Stage IIA, Stage IIB, etc.) at study entry
- Histopathological diagnosis grade (G1, G2, etc.) at study entry
- Baseline Eastern Cooperative Oncology Group (ECOG) performance status (PS)
- HER2 status (negative/positive)
- Progesterone receptor status (negative/positive)
- Estrogen receptor status (negative/positive)
- Baseline ER expression, Ki-67 index, and PR expression

6.5.3. Historical Illnesses/Pre-existing Conditions

Historical illnesses and pre-existing conditions (using Preferred Term(s) [PTs] from the most current version of the Medical Dictionary for Regulatory Activities [MedDRA®]) will be summarized.

6.6. Treatment Compliance

Treatment compliance information for all oral study drugs will be collected through pill counts. Compliance will be calculated as the ratio of total dose taken to the total assigned dose (minus any dose adjustments and doses omitted/withheld for medical or logistical reasons).

